- m. EOT assessments should be performed before the start of a new anti-tumor treatment.
- n. If the patient needs to start a new anti-tumor treatment within 28 days post last study medication administration, the safety follow-up assessments should be performed within 1 day before the start of the new anti-tumor treatment.

Table 2: Schedule of Assessments – Part 1 and Part 2

Assessments	Screening	Study Treatment Period							EOT ^u	Safety Follow up ^r	Disease Status FU ^s	Survival FU ^t
		Cycle 1				Cycle 2	Cycle 3	Subsequent cycles				
	Day -14 to 0	Day 1 (±0 day)	Day 8 – Part 1 (±1 day)	Day 8 – Part 2 (±1 day)	Day 15 (±1 day)	Day 1 (± 5 days)	Day 1 (± 5 days)	Cycle 4 Day 1, Cycle 5 Day 1, etc. (± 5 days)	EOT (+7 days)	28 days post last study medication administration (+7 days)	Every 6 weeks (from Cycle 1 Day 1) post EOT until disease progression (± 5 days)	Every 12 Weeks post disease progression (± 7 days)
Informed Consent	X											
Demographics	X											
Medical History	X											
Physical Examination	X	X	X			X	X	X	X	X	X	
Body Weight	X	X	X			X	X	X	X	X	X	
Vital Signs ^a	X	X	X			X	X	X	X	X	X	
12-Lead ECG	X	X ^b	X ^b			X ^b		X ^b		X ^b		
ECOG	X	X	X			X	X	X	X	X	X	
AE review ^c	X	X	X			X	X	X	X	X		
Prior and Concomitant Medication and Therapy	X	X	X			X	X	X	X	X		
Varlitinib Administration ^d		X ^d	X ^d	X	X	X ^d	X	X				
Capecitabine Administration ^e		X	X	X		X	X	X				
Urine or Serum β-HCG ^f	X								X			
Hematology ^g	X	X	X			X	X	X	X			

Assessments	Screening	Study Treatment Period							EOT ^u	Safety Follow up ^r	Disease Status FU ^s	Survival FU ^t
		Cycle 1				Cycle 2	Cycle 3	Subsequent cycles				
	Day -14 to 0	Day 1 (±0 day)	Day 8 – Part 1 (±1 day)	Day 8 – Part 2 (±1 day)	Day 15 (±1 day)	Day 1 (± 5 days)	Day 1 (± 5 days)	Cycle 4 Day 1, Cycle 5 Day 1, etc. (± 5 days)	EOT (+7 days)	28 days post last study medication administration (+7 days)	Every 6 weeks (from Cycle 1 Day 1) post EOT until disease progression (± 5 days)	Every 12 Weeks post disease progression (± 7 days)
Clinical Chemistry ^g	X	X	X			X	X	X	X			
Liver Function Test ^q				X	X							
Urinalysis ^g	X	X	X			X	X	X	X			
Coagulation ^{g,h}	X								X			
Serology ⁱ	X											
CA19.9 and CEA ^j	X						X	X ^j	X ^j			
Collection of tumor tissue ^k	X											
Biopsy ^l	X											
Pharmacokinetics ^m		X	X			X				X		
Biomarker Sampling ⁿ	X						X					
CT/MRI ^o	X ^p						X	X ^o		X		
Survival status contact											X	

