- Post-dose triplicate central 12-lead ECG at 3 hours post-dose

Cycle 3 Day 1 (± 5 days)

Refer to [Table 2](#) for assessment details and timing of the following assessments:

- Physical examination and weight
- Vital signs
- ECOG performance status
- Collection of AEs
- Concomitant medication review
- Blood collected for hematology and clinical chemistry
- Urine collected for urinalysis
- Varlitinib or placebo administration
- Capecitabine administration
- Blood collected for retrospective analysis of biomarkers
- Blood collected for CA19.9 and CEA
- CT/MRI of the chest, abdomen, and pelvis. Brain and/or bone lesions as applicable

Subsequent Cycles from Cycle 4 Day1, Cycle 5 Day 1, etc. (± 5 days)

Refer to [Table 2](#) for assessment details and timing of the following assessments:

- Physical examination and weight
- Vital signs
- ECOG performance status
- Collection of AEs
- Concomitant medication review
- Blood collected for hematology and clinical chemistry

- Urine collected for urinalysis
- Varlitinib or placebo administration
- Capecitabine administration
- Blood collected for CA19.9 and CEA every 6 weeks from Cycle 1 Day 1
- CT/MRI of the chest, abdomen, and pelvis. Brain and/or bone lesions as applicable every 6 weeks from Cycle 1 Day 1
- Post-dose triplicate central 12-lead ECG at 3 hours post-dose every 2 cycles from Cycle 4 Day 1

End of Treatment Visit (+ 7 days) – Part 1

- Physical examination and weight
- Vital signs
- ECOG performance status
- Collection of AEs
- Concomitant medication review
- Urine or blood collected for pregnancy test for female patients of childbearing potential
- Urine collected for urinalysis
- Blood collected for hematology, clinical chemistry and coagulation
- Blood collected for CA19.9 and CEA. If the reason for EOT is due to radiological disease progressions and CA19.9/CEA have already been assessed with the most recent scans, then CA19.9/CEA at EOT can be omitted.

EOT assessments should be performed before the start of new anti-tumor treatment.

6.2.3 Safety Follow-up Visit 28 Days Post Last Study Medication Administration (+ 7 Days) – Part 1

- Physical examination and weight
- Vital signs
- Triplicate central 12-lead ECG 3 hours after light snack
- Blood collected for PK analysis within 25 minutes after ECG evaluation
- ECOG performance status
- Collection of AEs
- Concomitant medication review

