- Absolute heart rate, pulse rate, QRS, QT/QTc values at 45 minutes pre-dose, 5 minutes pre-dose, 1, 2, 3, 4, 5, 6, 8.5, and 12 hours post dose
- Heart rate, pulse rate, QRS, QT/QTc change from baseline at 1, 2, 3, 4, 5, 6, 8.5, and 12 hours post-dose

QTc will be reported for both Fridericia and Bazett's corrections.

Triplicate ECGs will also be collected 3 hours post-dose Day 22 (Cycle 2 Day 1) and onwards every cycle while the subject remains in the study.

Due to the non-randomized, open label design of the Safety lead-in, data from the Safety lead-in will be presented separately from data from Part 1 of the study. Furthermore, ECG/QT outputs will be made available to the DSMB for consideration when determining whether the study should progress to Part 1.

Part 1

The Part 1 electrocardiographic Core ECG Laboratory assessments constitute the study's primary assessment of ECG/QTc. The time-based electrocardiographic analysis will be performed in Part 1 at baseline, Cycle 1 Day 1, Cycle 1 Day 8, and safety follow-up visit.

On Cycle 1 Day 1 and Day 8, the following parameters will be determined at the following time points:

- Absolute heart rate, pulse rate, QRS, and QT/QTc values at 45 minutes pre-dose, 5 minutes pre-dose, 1.5, 3, 5, 8 hours post-dose.
- Heart rate, pulse rate, QRS, and QT/QTc change from baseline at 1.5, 3, 5, and 8 hours post-dose.

Twenty-eight days after the last dose of study drug (after full drug washout), a set of triplicate ECGs will be collected 3 hours after a light snack.

In addition, triplicate safety ECGs will be collected 3 hours post-dose on Day 22 (Cycle 2 Day 1), Day 64 (Cycle 4 Day 1) and every 2 cycles while the subject remains in the

study. This data will not be analyzed by the Core ECG Laboratory but will be assessed by the investigator.

Part 2

ECGs will be collected in Part 2 of the study as part of standard safety monitoring at screening, baseline (before a snack), and 3 hours post-dose on Day 22 (Cycle 2 Day 1), Day 64 (Cycle 4 Day 1) and every 2 cycles while the subject remains in the study. These data will not be analyzed by the Core ECG Laboratory but assessed by investigators.

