- A summary of CTC grade 3 and above TEAEs attributed as *causally related to randomized* therapy sorted in descending order of frequency (i.e., most frequent event shown first). The order of frequency will be determined by the most frequent preferred term across both arms.
- Summary of SAEs by preferred term
- Summary of SAEs attributed as *causally related to randomized* therapy, sorted by preferred term
- Categorical Analysis of ECG findings (See [Section 8.5.2.3](#))

Additionally, the following will be listed:

- AEs with outcome of death along with the date of onset, dosing day, dose at onset, treatment status at onset (pre-treatment, ongoing or post-treatment) and Investigator's assessment of severity and relationship to study drug
- All SAEs along with the date of onset, dosing day, dose at onset, treatment status at onset (pre-treatment, ongoing or post-treatment), date of resolution (if AE is resolved), Investigator's assessment of severity and relationship to study drug
- AEs leading to discontinuation of study medication, listed along with the date of onset, dosing day, dose at onset, treatment status at onset (pre-treatment, ongoing or post-treatment) and Investigator's assessment of severity and relationship to study drug

If an AE is reported more than once during the study period, the greatest severity and the worst-case attribution will be presented in summary tables. Any AEs commencing > 28 days after discontinuation of study treatment will not be included in the tabulations of AE data.

All clinical laboratory data (clinical chemistry, hematology and urinalysis data), vital signs and ECG data will be listed. Data tabulations and graphical displays of clinical laboratory data (clinical chemistry, hematology, and urinalysis data), vital signs and ECG data, will include all assessments from screening up to (and including) 28 days after discontinuation of study treatment. In addition, all data measured on a continuous scale (except respiration rate and pulse) will be displayed graphically as described below:

Safety lead-in:

- Patient profile plots of laboratory data over time, including reference lines at the LLN and ULN. Any dose reductions will be indicated on the plots using a change in line-type.
- Patient profile plots of the change from baseline over time, including a horizontal reference line at zero. Any dose reductions will be indicated on the plots using a change in line-type.

Parts 1 and 2:

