### **3.2.1.1 General Considerations for Safety Assessments**

Missing safety data will not be imputed. However, safety assessment values of the form of “< x” (i.e., below the lower limit of quantification) or > x (i.e., above the upper limit of quantification) will be imputed as “x” in the calculation of summary statistics but displayed as “< x” or “> x” in the listings.

In order to produce data summaries by visit, visit time windows are required, and will be derived using the following conventions:

- The time windows will be exhaustive so that data recorded at any time point have the potential to be summarized. Inclusion within the time window should be based on the actual date and not the intended date of the visit.
- All unscheduled visit data should have the potential to be included in the summaries.
- The window for the visits following baseline will be constructed in such a way that the upper limit of the interval falls half way between the two visits (the lower limit of the first post-baseline visit will be Day 1). If an even number of days exists between two consecutive visits then the upper limit will be taken as the midpoint value minus 1 day.

Furthermore, the following principles will apply to the presentation of safety data:

- For summaries showing the maximum or minimum values, the maximum/minimum value recorded on treatment will be used (regardless of where it falls in an interval).
- For summaries of the ECG data, the mean value of the triplicate readings will be included in the summaries.
- Listings should display all values contributing to a time point for a subject.
- For visit based summaries:
  - If there is more than one value per subject within a time window then the closest value should be summarized, or the earlier in the event the values are equidistant from the nominal visit date. The listings should highlight the value for that subject that went into the summary table, wherever feasible.
  - For Parts 1 and 2 only, to prevent very large tables or plots being produced that contain many cells with sparse data, for each treatment group, visit data should only be summarized if the number of observations is greater than 1/3 of subjects dosed.

- For summaries at a subject level, all values should be included, regardless of whether they appear in a corresponding visit based summary, when deriving a subject level statistic such as a maximum.

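### Protocol 8.5.2.2 ends ECG and vital-sign tabulations at day 28, so a safety follow-up visit made on days 29 to 35, which the schedule allows, is left out; the SAP has no such limit

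*Protocol*

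**What the plan says.** **The limit.** Protocol 8.5.2.2 lists all laboratory, vital-sign and ECG data without a time limit. For tabulations and graphs it then sets one, covering laboratory data together with "vital signs and ECG data, will include all assessments from screening up to (and including) 28 days after discontinuation of study treatment". It applies to every study part.

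**The visit.** Tables 1 and 2 and Sections 6.1.4, 6.2.3 and 6.3.3 of the protocol set the safety follow-up at 28 days after the last study medication, with a +7-day window and no minus side. For Part 1 the heading of 6.2.3 reads "Safety Follow-up Visit 28 Days Post Last Study Medication Administration (+ 7 Days) – Part 1", and that visit includes "Triplicate central 12-lead ECG 3 hours after light snack". Section 7.1.1.7 gives this ECG a role in the main ECG assessment: "The time-based electrocardiographic analysis will be performed in Part 1 at baseline, Cycle 1 Day 1, Cycle 1 Day 8, and safety follow-up visit". The Synopsis and SAP 3.2 name the same visit as part of the primary electrocardiographic analysis.

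**The SAP.** Section 3.2.1.1 says: "The time windows will be exhaustive so that data recorded at any time point have the potential to be summarized". Section 7.7.2 follows the protocol paragraph closely but has no day-28 sentence. Section 7.7.3 summarizes ECGs at every scheduled assessment. Section 7.7.1 does keep the parallel 28-day limit for adverse events. Section 8, which records changes to the planned analysis, does not mention the difference.

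**Other timing statements.** The visit is brought forward if new anti-tumor treatment starts within 28 days (Table 2 footnotes and Section 6.2.3). Protocol 5.3.4 asks withdrawn or discontinued patients to attend within 28 days where possible. The clock also differs between places: discontinuation of study treatment (8.5.2.2), last study medication (Table 2 and 6.2.3), last dose of investigational product (6.4), last dose of varlitinib (Synopsis).

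**The concern.** The limit and the visit window meet on a single day. A patient seen on day 29, fully within the schedule, has an ECG and vital signs that appear in a listing but not in the protocol's tables or graphs.

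This matters most for the Part 1 washout ECG, which is the one scheduled reading that can show whether an ECG change seen on varlitinib plus capecitabine has gone after treatment. Under the protocol rule, the readings kept would be those on day 28 plus those brought forward because another therapy was about to start. The second group is selected, and its readings were taken before the stated 28 days.

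The effect differs by part:
- **Part 1:** washout ECG and follow-up vital signs.
- **Part 2:** follow-up vital signs only, because Section 6.3.3 lists no ECG.
- **Safety lead-in:** follow-up ECG (exploratory), vital signs, hematology and chemistry.

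A programmer working from the protocol and one working from the SAP would produce different follow-up tables.

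**Working it through.** The plan states no figure to reproduce. The check is a count of days, followed by a range under stated assumptions.

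**1. Permitted days (Table 2, Section 6.2.3).** Day 28 to day 28 + 7 = 35, so 35 − 28 + 1 = 8 days.

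**2. Days inside the limit (Section 8.5.2.2).** Day 28 only. Days 29 to 35 lie outside, which is 7 of 8. This assumes that discontinuation is dated to the last dose, so that both clocks start together.

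**3. Share of follow-up ECGs left out.** Let *e* be the share of visits brought forward before day 28 and *p* the share of the remaining visits made exactly on day 28. Then

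share left out = (1 − *e*) × (1 − *p*).

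The documents give neither *e* nor *p*. With *e* = 0:

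| Assumed timing | Calculation | Left out |
|---|---|---|
| All on day 28 | 1 − 1 | 0% |
| First working day from day 28, last-dose weekday uniform | 2/7 (day 28 falls on the weekday of the last dose, since 28 = 4 × 7; 2 of 7 are weekend days) | 28.6% |
| Half on day 28 | 1 − 0.5 | 50% |
| Even over days 28 to 35 | 1 − 1/8 | 87.5% |
| Even over working days in the window | (5 × 5/6 + 2 × 1)/7 | 88.1% |

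With even timing (*p* = 1/8), early visits lower the share: *e* = 20% gives 0.8 × 0.875 = 70.0%, and *e* = 40% gives 0.6 × 0.875 = 52.5%. It falls below half once *e* exceeds 1 − 0.5/0.875 = 42.9%. The logical range is 0% to 100%.

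**4. Possible knock-on.** In Parts 1 and 2, SAP 3.2.1.1 summarizes a visit for an arm only if more than 1/3 of dosed subjects have data. Suppose the protocol limit were applied together with this rule, with 60 dosed per arm (so more than 20 needed), all attending, and early visits still counted as the follow-up visit:
- even timing, no early visits: 60 × 1/8 = 7.5 remain, so the visit is dropped;
- even timing, 20% early: 12 + 48/8 = 18 remain, so it is dropped;
- even timing, 40% early: 24 + 36/8 = 28.5 remain, so it is kept;
- half on day 28, no early visits: 60 × 0.5 = 30 remain, so it is kept.

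**5. With the limit at day 35.** 0 of 8 permitted days fall outside.

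**The case against.** **The SAP already deals with it.** It has no ECG limit, uses exhaustive windows and names the follow-up visit in the primary ECG analysis. A team working only from the SAP would lose nothing. That is true, but neither document says that the SAP overrides the protocol here, and the SAP omits the rule without withdrawing it. The conflict remains.

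**The primary ECG analysis is not cut.** A reader might infer that the formal analysis loses its washout time point. The documents do not support that. The limit is worded for tabulations and graphs, while the between-arm comparisons and exposure-response models are in Section 8.5.2.3, which has no explicit limit. The change-from-baseline time points in 7.1.1.7 are 1.5 to 8 hours after dosing on Days 1 and 8, well inside it. What remains exposed is the descriptive part. The summaries by time point and the categorical summaries in 8.5.2.3 are themselves tabulations of ECG data, 8.5.2.2 cross-refers to the categorical ones, and nothing exempts them.

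**Visits may fall inside the limit anyway.** Day 28 is the named target, Section 5.3.4 asks some patients to attend within 28 days, and the clocks can diverge. Section 5.4.8.1 lets one drug continue after the other is withdrawn. It also requires permanent withdrawal only after more than 6 weeks of interruption, so discontinuation can be dated well after the last dose. This stands, and it is why no single percentage can be claimed. It also adds to what needs reconciling.

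**Early ECGs.** It is tempting to say that those taken before day 28 are not fully washed out. The documents support only that they precede the stated 28 days.

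**Conclusion.** The point holds as an inconsistency between a tabulation rule and a visit window, and between protocol and SAP. Section 8.5.2.2 excludes from tables and graphs any follow-up assessment on 7 of the 8 days that the schedule permits, including a Part 1 ECG that both documents treat as part of the primary time-based analysis.

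Its size is open. A reader might infer that most washout ECGs would be lost. That follows only if visits spread over the window (about 88%) and not too many are brought forward. It does not follow if sites book day 28 (0%) or the next working day (about 29%). All these figures assume that the two clocks coincide.

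Nor should the laboratory effect be extended to Parts 1 and 2, where no follow-up hematology, chemistry or urinalysis is scheduled. No data disappear from the listings. The correction is still worth making, because the rule as written drops scheduled data and the remedy costs very little.

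**What to change.** 1. In Protocol 8.5.2.2, extend the tabulation and graph limit for ECG, vital signs and laboratory data to include the safety follow-up visit through its full window, 28 + 7 = 35 days after the last dose.
2. State the same limit in SAP 7.7.2 and 7.7.3.
3. Use one clock start throughout, reconciling 8.5.2.2 with Table 2, Section 6.2.3, Section 6.4 and the Synopsis, and say how it is dated when one drug stops before the other.
4. Reconcile the within-28-days wording of Section 5.3.4 with the +7-day window.
5. Flag follow-up ECGs taken before day 28 because new therapy was starting, so that they can be shown separately.

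**Cost.** A few sentences in each document. The assessments are already scheduled and collected. The downside is that some readings taken up to a week later are tabulated. Because the schedule brings the visit forward only for therapy starting within 28 days, a few of these could follow a later start of new therapy, and the flag in item 5 can mark them too.

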8.5.2.3 ECG/QT Analysis

For the Safety lead-in, exploratory descriptive and categorical analyses, including change from baseline will be performed to investigate the impact of varlitinib and capecitabine treatments on the changes from baseline in ECG parameters.

For Part 1 of the study, a multi-step approach will be applied to evaluate the effect of capecitabine alone and varlitinib in combination with capecitabine on the ECG parameters at different time points post-dose. The comparisons will be done between ECG values at each time point post-dose and baseline and between treatment arms with and without varlitinib for each time point individually. The evaluation of the cardiodynamic effects of capecitabine and varlitinib may be explored using exposure-response modeling if there appears to be a meaningful effect of varlitinib when added to capecitabine on the ECG parameters including QTcF. This will be further described in the SAP.

Central Tendency Analysis will be performed for both the Safety lead-in and Part 1 of the study, the change from baseline in QTcF, PR, QRS, QTcB, and heart rate, will be summarized by time point (and treatment arm for Part 1) using descriptive statistics (n, mean, SD, min, median, max, 90% confidence intervals).

For both the Safety lead-in and Part 1, the following categorical data will be summarised:

- The proportion of patients obtaining treatment-emergent absolute QTcF values > 450 msec and \leq 480 msec; > 480 msec and \leq 500 msec; and > 500 msec
- The proportion of patients obtaining a QTcF increase from baseline values \geq 30 and <60 msec and \geq 60 msec
- The proportion of patients obtaining a QRS change from baseline > 25% resulting in QRS > 120 msec
- The proportion of patients obtaining a PR interval change from baseline >25% reaching a value >220 msec
- The proportion of patients obtaining a > 25% decrease from baseline in heart rate resulting in a heart rate < 50 beats per minute (bpm) or a > 25% increase from baseline in heart rate resulting in a heart rate > 100 bpm

For Part 1 of the study, the above categorical data summaries will be presented by treatment arm.

Following this, categorical analyses will be applied to the categorical data summaries above.

Additionally, T-wave morphology will be analyzed. The morphological T-wave analysis will be focusing on the change from baseline, i.e., treatment emergent changes.

Following Part 1 of the study, a formal statistical analysis will be performed to assess the potential impact of varlitinib and capecitabine on changes in the ECG parameters.

The statistical stepwise approach will be used to separate the cardiodynamic effect of varlitinib from normal circadian fluctuation in the ECG values and from the effect of capecitabine:

1. ANOVA mixed effects comparison of the absolute values of ECG parameters at each time point vs baseline using treatment as a fixed effect in order to evaluate the contribution of circadian fluctuation and

to determine how treatment differences contribute to the changes. The ECG parameter values will be log-transformed and the resulting output will include the geometric mean ratio for test vs reference with the corresponding confidence interval and p-value. Interaction term, time point x treatment, will be also evaluated if the data allow.

2. ANOVA comparison of the absolute values of ECG parameters as well as change from baseline (Δ ECG) between treatments for each post-dose time point assessed separately in order to separate the varlitinib effect from that of capecitabine. The ECG parameter values will be log-transformed and the resulting output will include the geometric mean ratio for test vs reference with the corresponding confidence interval and p-value. Δ ECG will be tested as untransformed and log-transformed parameters to avoid bias from discarding 0 Δ ECG values from the comparisons.
3. Exposure-Response Analysis: Linear mixed effect model between Δ QTcF and time matched concentrations of varlitinib and other potential metabolites if measured and as appropriate. Other ECG variable may be similarly analyzed and other models used, if appropriate.
 - 3.1 Δ QTcF will be calculated as the difference between each time point value and the average baseline value for each arm with the combination varlitinib/capecitabine treatment.
 - 3.2 $\Delta\Delta$ QTcF will be calculated for each patient in the combination arm individually as the difference between the Δ QTcF value for the arm with combination varlitinib/capecitabine treatment and the average value of all patients in the capecitabine alone arm matching time point. Other ECG parameters may also be used in the analysis including QTcB, heart rate, etc to provide supporting information.
 - 3.3 Base linear mixed effect model will include patients as a random effect.
 - 3.4 The total dose of capecitabine may be included as a fixed effect in the model to account for differences in total doses received by subjects with different body surface area.
4. Linear mixed effect model between Δ QTcF parameters and time matched concentrations of capecitabine and 5-FU (metabolite of capecitabine) and other potential metabolites if measured and as appropriate

- 4.1. $\Delta QTcF$ will be calculated for all patients in both arms as the difference between each time point value and the average baseline value.
- 4.2. Base linear mixed effect model will include patients as a random effect and treatment (capecitabine alone or in combination with varlitinib) as a fixed effect; the total capecitabine dose may also be used as a fixed effect.
5. Different covariates may be included in the complex models in addition to the base model as fixed effects such as time point in order to ensure the model feasibility and to evaluate covariates influential to ECG parameters.

The results of the fitted models will be presented using statistical parameters such as the geometric mean ratios and corresponding confidence intervals (for ANOVA) and estimates of the slope, and associated confidence interval for the linear mixed effect models.

In addition, the following graphic exploration of the exposure-ECG relationship may be performed:

- Residual plots to predict results
- Double Y plots with time on the X axis and time matched values of PK concentrations for varlitinib and capecitabine on the Y1 axis, ΔECG on the Y2 axis to determine the possibility of hysteresis between drug concentration and cardiodynamic effects
- Regression/scatter plots with time matched concentrations of varlitinib and capecitabine on the X axis and ΔECG on the Y axis
- Regression/scatter plots with varlitinib or capecitabine non-compartmental PK parameters of C_{max} , C_{trough} , AUC_{tau} and others on the X axis and maximum ΔECG on the Y axis
- Forest plots for different categories in ECG changes vs mean (SD) non-compartmental PK parameters for varlitinib or capecitabine on the X axis

